Aim 2. To assess the feasibility and acceptability of the optimized *MeSSSSage* intervention. In Phase 2 we will evaluate the feasibility and acceptability of two intervention components using a controlled 4-arm factorial design (n=160; 40 per arm): 1) real-time mobile voice information and support group alone, 2) asynchronous/on-demand text-based group support only, and 3) real-time mobile voice information and support group plus asynchronous/on-demand text-based group support. Feasibility and acceptability will be assessed via back-end data, surveys, and IDIs with purposively selected participants (n=30) and moderators.

Aim 3. To explore the preliminary effectiveness of the optimized *MeSSSSage* intervention components on six-month maternal and neonatal health outcomes. Phase 2 data will help us develop a preliminary understanding of the impacts of the intervention components on MCH health-related knowledge, behaviors and outcomes including exclusive breastfeeding, immunization, family planning uptake, postnatal visits, mental health and empowerment; however, it is not statistically powered to formally assess effectiveness.

This study is significant and innovative in addressing key priorities of NICHD's Pregnancy and Perinatology Branch and using systematic, user-centered and experience-driven design approach. These results will inform the most acceptable, feasible, and potentially efficacious intervention design to be robustly tested through an R01 mechanism to assess effectiveness for maternal and infant health outcomes, explore other research questions relevant to intervention development and scale-up for postnatal health among South Asian women, and explore generalizability across populations.

Significance

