Phase 2: Pilot test of optimized intervention, assessment of feasibility and acceptability (Aim 2) and preliminary effectiveness on maternal and infant health outcomes (Aim 3). After analysis of Phase 1 data, *MeSSSSage* will be adapted based on participant feedback and content will be expanded to cover topics relevant to the first six months of the postnatal period. If data from Phase 1 suggest that the tested mobile group forum modalities are not appropriate for this population, we will adapt our study protocol to explore other feasible means of providing information and support (e.g., SMS or video). We anticipate developing and testing two different modalities of postnatal education and support in a factorial design with an additional control arm for a total of four different group compositions. All women, including the control group, will receive the standard of care provided by the Government of India and described above. We will conduct a pilot test of the intervention using two groups per intervention modality for a total of eight separate groups, a total of 160 women (Table 2). Exact group structure and duration will be informed by Aim 1, but we anticipate the following:

Table 2: MeSSSSage components to be tested in feasibility and acceptability assessment (Phase 2).

	Arm 1	Arm 2	Arm 3	Control
Real-time live voice call group meeting: Interactive educational program with scripted didactic component plus discussion/question. Lead and moderated by health professional.	X		X	
Text-based, asynchronous, on-demand social support: App-based small group text-based communication. Moderated by health professional.		X	X	
Standard of care: 3 visits in the first 7 days postnatal (facility and home)	X	X	X	X

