Health-related behaviors (effectiveness)	Breastfeeding and complementary food introduction practices (breastfeeding initiation, length of exclusive breastfeeding, length of breastfeeding, timing of complementary food introduction), appropriate management of early childhood illnesses.
Health outcomes (effectiveness)	Early childhood immunization, postnatal depression and anxiety, postnatal family planning adoption.
Intervention perspectives (feasibility, acceptability)	Self-reported engagement in intervention components and topics, satisfaction with intervention components, likelihood of participating again, likelihood of recommending program, value on knowledge and social support gained from participation.

Analysis

Aim 2. Feasibility and acceptability of the optimized MeSSSSage intervention components. We will use a mixed methods approach, triangulating data from quantitative baseline and endline data, qualitative IDIs, and technology assessment. Feasibility and acceptability will be measured by participation rates at each session, trajectories of participation over time, and user engagement (via technology assessment backend data). Women's reports of use and satisfaction in the survey and the qualitative data will shed light on barriers and facilitators to participation. Moderator acceptability will be assessed by satisfaction, fidelity to topic/content based on protocol and perspectives on impact. We will test for differences in feasibility and acceptability between the three intervention arms to understand if both components (group meetings and text) or only one is the best approach, using ANOVA for continuous outcomes and chi-square or Fisher's exact tests, as appropriate, for categorical outcomes.

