Aim 3. Preliminary effectiveness of the MeSSSSage intervention components on six-month MCH outcomes. Using the quantitative survey data, we will statistically evaluate differences by study arm in improvements in women's knowledge, behaviors, and maternal and child health outcomes, compared to the control group (including effect sizes, controlling for relevant socio-demographics as necessary). Figure 1 displays the outcomes that are theoretically related to our intervention targets. Our main *knowledge* outcome will be a composite score representing the proportion of correct answers from a series of questions on knowledge of breastfeeding, newborn and infant care, maternal and infant danger signs, newborn care, and family planning, topics that will be covered within our interactive educational group component. Our main *behavior* outcome will be self-reported exclusive breastfeeding at 6 months. Our two main health related outcomes will be: (1) completion of early childhood immunization schedule; and (2) postnatal family planning uptake. We will also measure women's social support and related mental health status (depression and anxiety) using scales that have been previously validated in similar populations such as the Hopkins Symptom Checklist⁴¹ and the Multidimensional Scale of Perceived Social Support⁴². Finally, women's empowerment will be measured using decision-making and mobility scales.^{43,44}

Sample Size. This pilot development study is not formally powered to detect significant differences in outcomes, but will give insight into directionality of changes. The per group sample size was selected based on feasibility of recruitment, intervention delivery, and the interpersonal interaction important for a group-focused intervention. The sample is sufficiently large to assess the feasibility and acceptability outcomes through descriptive statistics.

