Document type: Statistical Analysis Plan

Study title: Development and Pilot Test of an mHealth Interactive Education and Social Support Intervention for Improving Postnatal Health – Phase 1

NCT number: NCT04636398

Document date: June 1, 2020

STATISTICAL ANALYSIS PLAN – PHASE 1

The proposed research includes two separate research phases to achieve our research aims: 1) To develop optimal intervention functions and mHealth technology delivery platforms for education and peer support among postnatal women in rural India; and to pilot test the optimized intervention and assess 2) feasibility and acceptability, and 3) preliminary effectiveness on maternal and infant health outcomes. Due to the exploratory nature of these aims, the sample sizes for our two study phases have been designed for feasibility, not for adequate power for statistical testing.

Phase 1. Phase 1 is a developmental research phase wherein we assess women's preferences for intervention functions, processes and platforms in order to design the most appropriate intervention for full piloting.

Data collection during this phase includes capture of back-end data for participation and content, and survey (all participants) and in-depth interview (subset of participants) to understand preferences.

Data includes:

- Backend data: intervention participation, intervention engagement, content of group discussions, content of text messaging.
- Survey: Preferences regarding group components, functions and modalities.
- In-depth interview: Preferences regarding group components, functions and modalities.

Quantitative data will be analyzed for means and proportions using STATA version 15. Text data from discussion/messaging and in-depth interviews will be analyzed for content and themes using Atlas.ti software.

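### Aim 2 asks whether both components or only one is best, but the three-arm omnibus tests it names cannot separate those two answers; pairwise differences with confidence intervals can.

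*Protocol*

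**What the plan says.** The Protocol (Analysis, Aim 2) states the task as follows: "We will test for differences in feasibility and acceptability between the three intervention arms". The purpose and the first method are given as "to understand if both components (group meetings and text) or only one is the best approach, using ANOVA for continuous outcomes"; chi-square or Fisher's exact tests are named for categorical outcomes. The paragraph gives no pairwise comparison, contrast, interval estimate or criterion for favouring one component or both. It does place the tests within a mixed-methods approach that also uses backend data, surveys and interviews.

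The design (Specific Aims, Aim 2) is a "controlled 4-arm factorial design (n=160; 40 per arm"). Table 2 gives voice to Arm 1, text to Arm 2 and both to Arm 3. Phase 2 is to be run with "two groups per intervention modality for a total of eight separate groups, a total of 160 women".

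On what the sample can support, the Sample Size section says: "The sample is sufficiently large to assess the feasibility and acceptability outcomes through descriptive statistics". The SAP says that the sample sizes of both phases "have been designed for feasibility, not for adequate power for statistical testing". The SAP's analysis text covers Phase 1 only and adds nothing on the Aim 2 tests.

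**The concern.** Whether both components or only one is best is a question about particular differences: what text adds to voice, what voice adds to text, and which single component is better if one is enough. A three-arm omnibus test answers a different question, namely whether any difference exists among the three. If it is significant, the plan has no next step that says where the difference lies. If it is not, the result is compatible with one component being enough and also with a worthwhile benefit of the combination that the pilot could not detect.

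The Sample Size section and the SAP both point towards description, while the Aim 2 paragraph specifies tests. For Aim 3 the Protocol promises effect sizes; for Aim 2 it does not. What is at stake is the design of the larger trial, which the Protocol says these results will inform.

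**Working it through.** **Inputs from the documents.** Three arms in the Aim 2 comparison; 40 women per arm (4 × 40 = 160); eight groups, two per condition, so 160/8 = 20 women per group. There is no power calculation to reproduce.

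**Inputs assumed, because the documents give none.** Alpha 0.05; effect sizes and rates as shown; no dropout; independent observations unless stated otherwise.

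**1. Can the F test separate the two answers?** Its power depends on the arm means only through the noncentrality λ = n·Σ(μᵢ − μ̄)²/SD², with 2 and 117 degrees of freedom. Take means for Arms 1, 2 and 3 in SD units.

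- Combined arm beats both single arms, (0, 0, 0.5): μ̄ = 1/6, and Σ = 1/36 + 1/36 + 4/36 = 1/6. λ = 40/6 = 6.67; power 62%.
- Text alone does as well as both, (0, 0.5, 0.5): μ̄ = 1/3, and Σ = 4/36 + 1/36 + 1/36 = 1/6. λ = 6.67; power 62%.

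The first state favours both components and the second favours one. The F test responds identically to each. This does not depend on the sample size, since n multiplies the same sum in both.

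The chi-square test behaves in nearly the same way, with λ = n·Σ(pᵢ − p̄)²/[p̄(1 − p̄)]:

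- 65/65/80%: 40 × 0.015/0.21 = 2.86.
- 65/80/80%: 40 × 0.015/0.1875 = 3.20.

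The small gap comes from the pooled variance, not from any sensitivity to which arm is best.

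**2. How often would the omnibus test be significant?** One arm better, the other two equal, 40 per arm:

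| ANOVA, gap in SD | Power |
|---|---|
| 0.2 | 14% |
| 0.3 | 26% |
| 0.4 | 43% |
| 0.5 | 62% |
| 0.6 | 79% |
| 0.8 | 96% |

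| Chi-square, arm rates | Power |
|---|---|
| 50/50/60% | 14% |
| 65/65/80% | 31% |
| 60/60/80% | 49% |
| 70/70/90% | 58% |
| 60/60/85% | 70% |
| 50/50/80% | 82% |

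ANOVA power passes 50% at about 0.44 SD and 80% at about 0.61 SD. Chi-square power passes 50% at a gap of 18 to 21 points for base rates of 50% to 70%.

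**3. What would a pairwise interval look like?** For a continuous measure, the 95% half-width is 1.96 × √(2/40) = 0.44 SD. For 80% v 65% it is 1.96 × √(0.65 × 0.35/40 + 0.80 × 0.20/40) = 1.96 × √0.0096875 = 0.193, or ±19 points.

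**4. Allowance for groups.** With groups of 20, the design effect is 1 + 19 × ICC. The ICC is assumed.

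- ICC 0.01: design effect 1.19; 0.193 × √1.19 = 0.21, or ±21 points.
- ICC 0.05: design effect 1.95; 0.193 × √1.95 = 0.27, or ±27 points.

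**5. Is an estimate-based reading workable at this size?** By simulation with independent observations, the arm with the highest observed mean is the truly best arm in about 85% of trials at a 0.3 SD advantage and 98% at 0.5 SD.

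**The case against.** The strongest reply is that this is a pilot which says openly that it is not powered. Its Sample Size section assigns feasibility and acceptability to descriptive statistics, and arm-level means and proportions can show which arm is ahead whatever the F test says; step 5 supports that. Phase 2 is also provisional: its structure is described as anticipated, and the Timeline sets aside a period for modifications before it starts. Nothing in the Aim 2 paragraph forbids pairwise follow-up.

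Most of this stands, and it rules out two stronger readings that a reader might infer.

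- **That the tests will usually be non-significant even when one arm is better.** The documents state no effect size, rate or alpha, so they do not support this. It is true for gaps below about 0.44 SD or 18 to 21 points and false above them: 79% power at 0.6 SD, 96% at 0.8 SD.
- **That the choice of approach rests on these tests.** The Aim 2 paragraph triangulates surveys, interviews and backend data, and no passage makes a p-value the selection rule or treats non-significance as evidence of no added value.

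What the reply does not meet is the mismatch in step 1. Disclosing low power is an argument for estimation, whereas the paragraph specifies tests. Those tests are the only between-arm quantitative comparison named for Aim 2, and they do not address the stated question at any sample size.

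**Conclusion.** The point holds in this form: the omnibus tests named for Aim 2 cannot distinguish a combined arm that is best from a single component that is enough, and a non-significant result would not show that one component suffices. The first part is exact for the F test and needs no assumption about effect size, sample size or alpha. Specifying tests also sits poorly with the Sample Size section's reliance on descriptive statistics.

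The power figures are secondary and conditional on alpha 0.05, independence and full follow-up. With 32 women per arm (20% dropout), power at 0.5 SD falls from 62% to 52%. Because lack of power is disclosed and other evidence feeds the judgement, the change should be made but does not put the pilot in doubt.

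**What to change.** In the Protocol's Aim 2 analysis, make the primary quantitative comparison three estimated differences, each with a 95% confidence interval:

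- Arm 3 minus Arm 1: the value of adding text to voice.
- Arm 3 minus Arm 2: the value of adding voice to text.
- Arm 1 versus Arm 2: which single component, if one is enough.

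Limit each to measures that both arms share, such as satisfaction and likelihood of taking part again or recommending the programme (Table 3). Arm 2 has no voice meetings and Arm 1 no text group, so describe session attendance and text posts only in the arms that have that component.

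Treat any omnibus p-value as exploratory, and state that non-significance will not be read as no added value. State also that intervals assuming independence are too narrow if outcomes correlate within the two groups per arm, and show the widening over a range of assumed ICCs, as in step 4.

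The cost is a few sentences and slightly more reporting on the same data. The intervals will be wide, which reflects what 40 women per arm in two groups can show.

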2. We extend the solid evidence base for group care in pregnancy to the postnatal period, a neglected and vital period for infant health outcomes, as well as maternal mental and physical health outcomes. Postnatal care is especially challenging in settings like rural India where women live far from facilities, have restrictions on physical mobility, and practice seclusion after childbirth.

The approach taken in this research will add to the scientific understanding of whether mHealth interventions can successfully include group components and interaction between users. It will also expand our toolkit of approaches for intervening in the postnatal period, with applications for other times in the life course and populations. If proven successful, this study will lead to the development of a tested tool ready for next steps in scale up process to robustly test effectiveness that is likely to improve both maternal and infant health outcomes.

Approach

The mobile platform we will be adapting was developed by members of our IIIT-Delhi team, and has been tested with the implementing partner (SWACH). This innovative platform provides a single collaborative learning environment that is optimized for use by both basic feature phones and smartphones. This simultaneously lowers the cost and increases the reachability while accommodating increasing technology access. The back-end of the systems is built on Interactive Voice Recognition (IVR) technology that allows easy data collection that can then be used for analysis on user participation. Moreover, the system allows the storage of the knowledge generated in an interactive session. Recently the system has been extended by applying state-of-the-art natural language processing techniques to extract the audio and create a knowledge base which can then be used to deliver automated answers.³⁸ It has previously been tested for feasibility with SWACH in the general population, and as a training for health workers and found improvements in health worker knowledge.^{35,39} Members of the team have also developed a platform similar to WhatsApp that may be integrated into this design or added on to support the MeSSSSage design.

Study Site and Population: This study will occur in Kurukshetra district, Haryana state, India. Household mobile phone ownership is high, with 90% of households, and 50% of women, in this district owning a mobile phone.⁴

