Technology assessment: Finally, we will collect and analyze the quantitative backend data from the prototype to gain more insight into women's participation in the intervention, including attendance and level of participation in group interactive educational sessions, use of mobile social support platform (number of posts, frequency, topic), etc. Text data from transcripts of the educational sessions and content of group messaging will be analyzed for content in order to understand primary educational needs and interests for postnatal women.

Group moderator survey and interview: ASHA facilitators moderating the groups will be asked to respond to a short questionnaire after each group session to understand: preparation and delivery time, content, efficiency, acceptability and satisfaction with the group model, perspectives of impact, challenges, and any follow-up/referral necessary.⁴⁰ Regarding facilitation of groups that receive the text-based messaging intervention component only, ASHA facilitators will report on experiences in the prior week. We will also conduct monthly semi-structured interviews with each of the ASHA facilitators to understand their own preferences around the group components, their experiences preparing for and conducting the sessions, and their perspectives on mobile provision of education, care, and support.

Measures: The baseline survey content will include sociodemographic characteristics and knowledge about maternal and infant health, self-efficacy, and perceived social norms regarding MCH-related health promoting behaviors. The endline survey will include acceptability questions such as women's satisfaction with and perceptions of MeSSSSage, maternal and infant knowledge-, behavior-, and health-related questions including about breastfeeding, complementary food introduction, immunization, family planning uptake, maternal physical and mental health, etc. which have previously been used in this setting (Table 3)⁴.

Table 3: Participant survey measures (Phase 2)

Category	Measures
Sociodemographic characteristics	Age, age at marriage, educational attainment, caste, language spoken, household assets, women's status/decision-making, social support and relationship quality.
Health-related knowledge (effectiveness)	Knowledge on maternal and neonatal danger signs, best practices for infant care, family planning.

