Recruitment and retention. The research team has successfully conducted research among women in the postpartum period living in this area, and have been successful in recruitment and retention. We do not anticipate challenges to recruitment of study participants or retention during the full study period. If women appear to be lost to participation, the local ASHA will be notified and she will follow up with the woman participant to determine the barriers to her participation in the intervention.

Gender gaps in mobile phone access. While mobile phone penetration is increasing dramatically across all of India, significant gender gaps exist in ownership and use of mobile technologies. For example, among the adult population, 84% of males are considered primary mobile phone owners compared to 65% of females.³⁴ Younger individuals have higher mobile phone ownership than older individuals; our target population of primiparous women is likely to fit within an age group of higher mobile ownership. We will provide participants who do not personally own their own phone with a phone to reduce barriers to participation resulting from multiple household phone users, and will provide airtime for the study to all participants.

Low literacy among target population. Recent data from Haryana state show that 75% of women of reproductive age are literate⁴, and thus it is possible that women's low overall literacy, and potentially low technological literacy, will reduce their ability to engage in *MeSSSSage*. However, the research team's experience has not found this to be a problem for prior research projects among the target population. Additionally, given the young age of participants, we anticipate that they will be more literate and tech-savvy than average. Our experience of our team in the field at this specific study site has found that WhatsApp is extensively being used for communication and husbands are more actively involved in pregnancy and can support their wives. The *MeSSSSage* platform will allow illiterate women to speak to answer questions, thus making it more accessible to low literacy women. At enrollment, the research assistants will provide one-on-one training participation in the group meeting and text-based components of the intervention, including basic instructions on texting. Given the population we seek to generalize our findings to, we will not exclude illiterate women from this study.

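### The Aim 2 arm comparisons use valid tests that take no covariate, giving up modest precision and protection against chance imbalance in schooling and phone source

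*Protocol*

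**What the plan says.** Phase 2 is a "controlled 4-arm factorial design (n=160; 40 per arm"), so the Aim 2 comparison of the three intervention arms involves 3 × 40 = 120 women. The Protocol's Analysis section, under Aim 2, gives the purpose and methods of that comparison as "to understand if both components (group meetings and text) or only one is the best approach, using ANOVA for continuous outcomes and chi-square", and names Fisher's exact test as the alternative for categorical outcomes. No covariate is mentioned. Baseline data come in only through a general statement that several data sources will be triangulated.

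Adjustment does appear in the next paragraph, under Aim 3: "controlling for relevant socio-demographics as necessary". That clause is attached to the effectiveness outcomes and is not carried back to Aim 2. The SAP covers the Phase 1 analysis only and adds no Phase 2 model. Phase 2 allocation is by random number generator, with no stratification stated.

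The relevant baseline information is largely in hand. Table 3 lists "Age, age at marriage, educational attainment, caste, language spoken, household assets" among the sociodemographic measures, and the baseline survey takes place at enrolment. Phones go to women who lack one, but phone source is not a Table 3 item.

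Under Potential problems, the Protocol raises the possibility that low literacy "will reduce their ability to engage in" the programme. On phones it says: "We will provide participants who do not personally own their own phone with a phone to reduce barriers to participation".

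**The concern.** Participation and engagement are the core Aim 2 outcomes, and the Protocol itself singles out two baseline factors that might drive them. Tests without covariates leave whatever those factors explain in the error term. With 40 women per arm and no stated stratification, the arms can also differ by chance in schooling or phone source, and an unadjusted comparison carries that difference into the estimated arm effect. One of the two components is text-based, so literacy is a natural factor to want balanced.

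What is at stake is how clearly Phase 2 can say whether both components or only one should go forward to the larger trial.

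**Working it through.** **What there is to reproduce.** The Protocol states no alpha, power, effect size, SD or expected dropout, and says the pilot is not formally powered. There is therefore no power figure to reproduce. The counts agree: 4 × 40 = 160, and eight groups of 20 = 160.

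**Inputs from the Protocol.** 40 women per arm; three arms compared; phone ownership "with 90% of households, and 50% of women, in this district owning a mobile phone" (Study Site and Population); 75% of women of reproductive age in the state literate (Potential problems), used as a stand-in for schooling.

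**Assumed inputs.** Two-sided 5% level, no dropout, independent women, effect size f = 0.25, and a share R² of outcome variance explained by schooling and phone source together. The documents give no R², so a range is shown.

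**Precision.** Equivalent women per arm = 40 / (1 − R²). Three-arm power comes from the noncentral F distribution with noncentrality 120 × 0.25² / (1 − R²), on 2 and 117 degrees of freedom (2 and 115 with two single-parameter covariates). The 95% half-width for a pairwise difference is 1.96 × √(2(1 − R²)/40) SD.

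| R² | Equivalent women per arm | Noncentrality | Power at f = 0.25 | Half-width (SD) |
|---|---|---|---|---|
| 0 (as planned) | 40 | 7.50 | 67.6% | 0.438 |
| 0.05 | 42.1 | 7.89 | 69.9% | 0.427 |
| 0.10 | 44.4 | 8.33 | 72.4% | 0.416 |
| 0.20 | 50.0 | 9.38 | 77.7% | 0.392 |
| 0.30 | 57.1 | 10.71 | 83.3% | 0.367 |

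**Which R² is plausible.** Suppose 25% of women cannot read and their use is 40 percentage points lower (assumed), with overall use near 50%. Then R² = 0.40² × 0.25 × 0.75 / (0.50 × 0.50) = 0.03 / 0.25 = 0.12. A gap that large in one factor still gives only 0.12, so 0.30 is demanding and 0.05 to 0.20 is the range to rely on.

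**Chance imbalance.** With three independent binomial counts of 40, the highest and lowest arms differ by 15 points or more in 33% of randomisations at 75% literacy and in 43% to 44% at 50% phone ownership. By 20 points or more, the figures are 13% and 21%. For one named pair of arms, a gap of 15 points or more occurs in about 15% and 22%.

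**Effect on the test.** In simulated three-arm trials with no true difference, with R² split equally between the two factors, unadjusted ANOVA rejects in 4.7% to 4.8% over all randomisations. In the 21% with a phone gap of 20 points or more, it rejects in 5.4%, 5.9% and 6.9% at R² of 0.05, 0.10 and 0.20 (8.1% at 0.30). The adjusted model stays at 4.9% in those same trials. A 20-point phone gap by itself moves the unadjusted arm difference by 0.20 × √((R²/2)/0.25), which is 0.06, 0.09 and 0.13 SD at R² of 0.05, 0.10 and 0.20.

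**Clustering.** Each arm has two groups of about 20. With intraclass correlation ICC, the variance of an arm mean is inflated by 1 + 19 × ICC. If the covariates act only within groups, adjustment cuts that variance by R² / (1 + 19 × ICC) instead of R². At an assumed ICC of 0.05 and R² of 0.20, this is 0.20 / 1.95 = 10%, about half the gain in the table.

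**The case against.** A reader might infer that the unadjusted tests are invalid, or that chance imbalance biases the choice of components. The documents and the calculation do not support that. Allocation is random, error over all randomisations is about 5%, and the p-value already allows for chance imbalance. The distortion exists only conditionally on an imbalance that has occurred, and it is small at plausible R².

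A reader might also take the Protocol to say that literacy and phone access are strong determinants of use. It does not. It calls literacy a possible barrier, reports that the team has not found it a problem in earlier projects, expects these young women to be more literate than average, notes that the platform lets women who cannot read respond by voice, and provides one-on-one training. Phones and airtime are supplied in order to remove the other barrier. Both effects may therefore be small. The imbalance inputs are on the high side too: at an assumed 10% unable to read, the chance of a 15-point range falls from 33% to about 10%, and at the 65% female ownership quoted under Potential problems the phone figure is 40%.

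Nor does one test decide the design. Aim 2 draws on surveys, interviews and back-end data, the Sample Size paragraph presents the sample as enough for descriptive assessment, and Phase 2 details are provisional until Phase 1 reports.

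Finally, clustering is the larger threat. At an assumed ICC of 0.05, plain ANOVA with two groups of 20 per arm has a type I error of about 22%, and individual covariates do not cure that.

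All of this stands, and it limits the size of the point. It does not remove it: the Protocol still plans between-arm tests to judge the components, and a better use of baseline data is nearly free.

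**Conclusion.** The point holds as a modest matter of efficiency and interpretation. Across R² of 0.05 to 0.20, adjustment is worth 2 to 10 extra women per arm and about 2 to 10 points of three-arm power at f = 0.25. It also keeps the error rate near 5% in randomisations with a marked phone imbalance.

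These figures rest on an R² and an effect size that the documents do not give, and on independence between women, which the group format makes doubtful. The realised gain will be smaller once groups are accounted for. The change is worth making because it costs little and fixes the covariates before any outcome is seen.

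**What to change.** In the Aim 2 analysis paragraph:

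- **Continuous outcomes.** Replace one-way ANOVA with a linear model containing arm, educational attainment and own versus study-supplied phone, all named in advance. State one coding for schooling, such as years or a single binary cut, since a multi-category coding uses more degrees of freedom.
- **Categorical outcomes.** Keep chi-square or Fisher's exact test, and add covariate-standardised risk differences where event counts allow. Replacing Fisher's test outright with logistic regression is not advised: with 40 women per arm, the model can fail when an outcome such as satisfaction is near 0% or 100%.
- **Data.** Add phone source to the baseline row of Table 3, recorded before allocation is known. Define it once, because the Phase 2 procedures refer to women without a phone while the Potential problems section refers to women who do not personally own one.
- **Reporting.** Show unadjusted arm summaries alongside. Combine the model with whatever handling of groups is adopted, because covariates do not substitute for it.

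Cost: a few lines of wording, one yes/no field, and two degrees of freedom out of 117 if schooling takes a single term. No extra visits or participants are needed. The Phase 2 preparation quarter in the Timeline, which already provides for tool development and ethics modifications, is a convenient point to make the change.
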